5.9. Checks of Validity and Robustness

Confirmatory analyses for the primary and secondary endpoints are detailed in Section 5.2 and Section 5.3.

5.10. Subject Characteristics and Disposition

The following subject demographic characteristics will be summarized by treatment group for the FAS:

- Age
- Height, weight, body mass index (BMI)
- Race

- Ethnic origin
- Baseline 1-hr pad weight
- Baseline 24-hr pad weight
- Baseline 3-day voiding diary pads used and incontinence episodes
- Baseline I-QOL scores

Descriptive statistics for age, height, weight, BMI, 1-hr pad weight, 24-hr pad weight, 3-day voiding diary data, and I-QOL scores will include N, mean, standard deviation, minimum value, median, 25th and 75th percentiles (not for age and BMI), and maximum value.

Descriptive statistics for race and ethnic origin will be number (n) and percent (%).

A separate summary of Age, Race, and Ethnic origin will be provided for subjects who were classified as screen failures.

A summary of medical, sexual and gynecological history by treatment group, using the FAS, will also be provided.

Subject disposition will be summarized by treatment group, for all screened subjects. This summary table will include the total number of subjects screened, the reason for screen failure (n and % of subjects for each reason); the n and % of subjects randomized, and the n and % of subjects included in the FAS, PPP and SP; the n and % of subjects completing the study and withdrawing from the study, and the reason for early withdrawal. The determination of the placement of each subject into the different populations, such as those who complete the study, those who withdraw from the study, the FAS, the SP, etc will be done prior to treatment unblinding at the end of the study. A separate listing will include the reason for screen failure for subjects who were classified as screen failures.

Investigational product administration will be summarized in the SP by treatment group using summary statistics. The number of treatment pulses used, as well as the reasons for deviation from the treatment schedule will be listed.

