5.1.1.1 Full Analysis Set

The Full Analysis Set (FAS) is defined as all randomized subjects who have 1-hour pad weight data at both Baseline and 5 months post-treatment. The FAS will be used for all of the efficacy analyses.

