5.1.1.3 Safety Population

The Safety Population (SP) includes all randomized subjects in whom the treatment procedure is started, regardless of if the procedure is completed. The SP will be used for all of the safety summaries.

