5.4. Statistical Analyses of Safety Measures

No statistical analyses will be performed on any of the safety data in this study. The SP will be used for all safety summarizations, with subjects included in the treatment group they actually received regardless of their randomized treatment group. AEs will be coded using definitions in the most recent version of Medical Dictionary for Regulatory Activities (MedDRA; Version 23.0). Each AE will be coded with its appropriate Preferred Term (PT), and linked with its associated System Organ Class (SOC). Based Section 3.3.2 of the Study Protocol (Section 4.1.3 of this document) all AEs are by definition treatment emergent (TEAE) so the term AE is equivalent TEAE. AEs will be summarized by SOC, severity, and relationship to study treatment for each treatment group.

No descriptive statistics are planned for vital signs or safety laboratory measurements, but data will be available in a listing. Screening data for the physical/pelvic/neurological examination will also not be summarized but will be provided in a listing.

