5.7. Handling of Dropouts and Missing Data

Subjects who discontinue the study prior to completion will not be replaced. Missing data will be considered left as missing.

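### Baseline and history tables are planned only for the FAS, so any randomized subject without a Month 5 1-hour pad weight appears in no baseline summary, even if counted in the safety tables

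*SAP*

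**What the plan says.** SAP section 5.10 fixes the population of two sets of tables. For demographics and baseline measures (age, body size, race, ethnic origin, both pad weights, diary counts, I-QOL) it says: "The following subject demographic characteristics will be summarized by treatment group for the FAS". For history it says: "A summary of medical, sexual and gynecological history by treatment group, using the FAS, will also be provided".

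Section 5.1.1.1 defines the FAS as "all randomized subjects who have 1-hour pad weight data at both Baseline and 5 months post-treatment". Section 5.1.1.3 defines the Safety Population (SP) differently: it "includes all randomized subjects in whom the treatment procedure is started, regardless of if the procedure is completed". It adds: "The SP will be used for all of the safety summaries". Section 5.4 repeats this and sets the grouping, "with subjects included in the treatment group they actually received regardless of their randomized treatment group".

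Three other provisions bear on the point:

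- Section 5.7: "Subjects who discontinue the study prior to completion will not be replaced". Missing values stay missing.
- Section 5.10, on subjects who never entered the trial: "A separate summary of Age, Race, and Ethnic origin will be provided for subjects who were classified as screen failures".
- Section 5.10 also plans a disposition table for all screened subjects, and a summary of product administration on the SP.

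**The concern.** A baseline table normally answers two questions: were the arms comparable when randomized, and who was exposed to treatment? A table restricted to subjects with a Month 5 outcome fully answers neither, because membership depends on something that happens after treatment. Loss that differs by baseline severity or gynecological history could hide an imbalance present at randomization, or produce one that was not there.

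The baseline and adverse event tables can also rest on different subjects. A woman who is treated, has an adverse event and withdraws before Month 5 is counted in the adverse event table, but her age, baseline leakage and history are in no summary by arm.

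The restriction serves no purpose for these variables. They describe the subject at entry, and none needs a Month 5 value to be tabulated. The label makes misreading easier: the SAP's abbreviation table equates the FAS with intent-to-treat, so a reader could take the FAS baseline table to cover everyone randomized.

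**Working it through.** The SAP states no figure on this point, so the check compares definitions and then counts.

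**Step 1: who is in which table.** The 1-hour pad weight at Baseline is an entry requirement (section 5.1), and randomization follows confirmation of eligibility (section 5.6.2). For an eligible randomized subject, FAS membership therefore turns on the Month 5 value.

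| Randomized subject | FAS | SP | Baseline and history summary | Adverse event tables |
|---|---|---|---|---|
| Procedure started, Month 5 1-hour pad weight present | yes | yes | yes | yes |
| Procedure started, withdraws before Month 5 | no | yes | no | yes |
| Procedure started, stays in study but misses the Month 5 pad test | no | yes | no | yes |
| Procedure never started, no Month 5 pad weight | no | no | no | no |

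Nothing else in the SAP fills the empty cells in the baseline column. The disposition table gives counts and reasons, not characteristics. The screen-failure table covers subjects who were not randomized. The product administration summary is on the SP but describes treatment delivered.

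**Step 2: size per subject.** Inputs from section 5.6.1: about 36 randomized, 12 per arm. Assume all 36 are treated, and let k be the number without a Month 5 1-hour pad weight. The share of the SP in no baseline table is k/36. If all k fall in one arm, that arm's share is k/12.

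| k | k/36 | k/12 (all in one arm) |
|---|---|---|
| 1 | 2.8% | 8.3% |
| 2 | 5.6% | 16.7% |
| 3 | 8.3% | 25.0% |
| 4 | 11.1% | 33.3% |
| 6 | 16.7% | 50.0% |

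**Step 3: how many to expect.** The SAP gives no dropout rate. Take a loss probability q from 5% to 20% as an assumption.

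- Expected number: 36 × 0.05 = 1.8 and 36 × 0.20 = 7.2, so about 2 to 7 subjects.
- Chance of at least one, if losses are independent: 1 − (1 − q)^36. At q = 0.05 this is 1 − 0.95^36 = 84%. At q = 0.20 it is 1 − 0.80^36, above 99%.
- Expected share of treated subjects who are in both sets: 1 − q, that is 95% down to 80%.

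**Step 4: effect on inference.** The baseline and history tables feed no test. The efficacy models in sections 5.2 and 5.3 use the FAS however section 5.10 is written, and section 5.4 plans no statistical analysis of safety data.

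**The case against.** The strongest reply is that a FAS baseline table is legitimate and the gap is small. All efficacy analyses use the FAS, so a table of that set shows the balance of the subjects actually compared, and would reveal an imbalance in that set created by loss. This stands, and is a reason to keep the FAS table. It does not show balance as randomized, or what the treated group looked like.

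Second, the loss is partly visible. The disposition table reports by arm how many subjects are in each population, and why subjects withdrew. This also stands: the number lost per arm can be read. What cannot be read from the summaries is whether those lost differed at baseline.

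Third, the gap arises from how the FAS is defined; an FAS of all randomized subjects would largely remove it. True, but section 5.10 makes its own choice of table population, and can be corrected without touching the efficacy set.

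Fourth, the separate table shells (section 5.11.1) are not at hand, and listings may cover these subjects. That cannot be judged here. Section 5.10 nevertheless names the FAS explicitly for both sets of tables, and a listing is not a summary by arm.

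A reader might infer that treated early leavers are the only subjects left undescribed. The definitions do not support that: subjects randomized but never treated, and those who only miss the Month 5 pad test, are left out too. A reader might also infer that adverse event rates cannot be interpreted at all. That goes too far, since at the assumed losses 80% to 95% of treated subjects are expected to be in both sets.

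**Conclusion.** The point holds as a reporting weakness. Followed as written, section 5.10 leaves every randomized subject without a Month 5 1-hour pad weight out of all baseline and history summaries, while those whose procedure was started remain in the safety tables. Balance between arms is shown only after post-treatment loss. Whether loss was selective on baseline characteristics cannot be seen from the summaries, and the denominators of the baseline and adverse event tables can differ.

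Each such subject is 8.3% of an arm of 12. The total of about 2 to 7 of 36 rests on an assumed 5% to 20% loss and on all 36 being treated; three losses falling in one arm (25%) is an illustration, not a forecast. With no loss, and everyone treated as randomized, the FAS and SP tables coincide and the gap is nil.

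This point should not be read as saying that the primary or any secondary test is altered. No efficacy result depends on the population of these tables.

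**What to change.** In section 5.10, replace the FAS restriction for demographics, baseline measures and medical, sexual and gynecological history with:

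1. a summary for all randomized subjects, by randomized group;
2. a summary for the SP by treatment received, where SP membership or grouping differs from the randomized set;
3. the existing FAS summary, kept beside the efficacy results.

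This needs SAP wording and a rerun of the existing tables, with no new data and no additional subjects. The downside is a few extra table pages, for up to three populations. If every randomized subject is treated as assigned, item 2 is not needed; if all also have a Month 5 pad weight, one version serves for all three.

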5.11. Identification of Subgroup and Session Factors

Study site will be used a factor in all ANCOVA analyses as previously discussed in Sections 5.2 and 5.3. Data Tables and Listings

5.11.1. Templates of Tables

Table templates and listing templates are found in the separate Table Shells Plan.

5.12. Derived Variables and Derived Files

5.12.1. Questionnaire Scoring

The scoring of the I-QOL questionnaire is addressed in a separate questionnaire scoring document. This is the document developed for the initial SUI protocol, VI-17-01.

5.12.2. Coding

Medical history and AEs will be coded using MedDRA version 23.0. Concomitant medications will be coded using WHO-Drug Dictionary Enhanced (WHO-DDE) format B3 from the March 2020 release.

